## Statistical methods

The outcome variables (rate of torque development 0-100 ms, 0-200 ms, peak RTD, time to peak RTD, time to peak torque for both knee extension and knee flexion, respectively) will be compared between groups using an unpaired two-sided students t-test, assuming the residuals will be normally distributed, otherwise the non-parametric alternative, the Wilcoxon rank sum test, will be used. The alfa and beta-1 level will be set for 5% and 80%, respectively.

As outcome variables have been a priori specified and prioritized, and also analyzed and reported in the pre-specified order, no corrections for multiple testing will be applied. Data will be reported with between-group differences, standardized effect sizes based on Cohens d, exact p-values, and 95% confidence intervals. All data inspection, analysis, and visualizations will be conducted using R (R Foundation for Statistical Computing, Vienna, Austria), in the jamovi interface (The jamovi project 2023, version 2.4.1). All r-code and full data set will be shared with journal publication or in an open-access repository.

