## Methods

The study design and analysis strategy have been published along with a trial registration (ClinicalTrials.gov NCT05789095). The study will include 13 adolescent participants with Osgood-Schlatter and a group of 13 pain free controls matched on sex, age, and sports participation on the group level. Testing will include bilateral rate of torque development measurements of knee extension and flexion, with a fixated handheld dynamometer, during a single test-session lasting approximately two hours. The examiner responsible for strength-testing will be blinded to case-status. Along with anthropometric data, participants will perform the anterior knee pain provocation test to assess pain-response to sustained knee loading, a countermovement jump test to assess power and jump height, and provide patient-reported measures of condition severity, pain, disability, and quality of life. Data collection will start February 2023 and is expected to be completed by May 2023.

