## Methods

### Study design

In this study we will include adolescent participants with Osgood-Schlatter, presenting as anterior knee pain localized to the tibial tubercle (OSD-group), and a matched group of pain free controls (control group), matched on sex, age (<1 year group difference) and type of sports (weightbearing vs non-weightbearing). The study will be conducted at the International Olympic Research Center - Copenhagen (Sports Orthopaedic Research Centre - Copenhagen), at Hvidovre University Hospital. The project will be initiated March 2023, with recruitment of 26 participants: 13 participants in the OSD-group, and 13 in control group.

Approval has been obtained from the ethical review board of the Capital Region of Denmark (H-20072873), and the Data Management Agency of Capitol Region of Denmark (P-2021-73).

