### Outcome measures

The outcome measures are rate of torque development and NRS-values in relation to the force-measurements. To calculate the rate of torque (Nm/s/kg), the rate of force development-variables (N/s) is multiplied with length of the lever (m) and divided with the participant's bodyweight (kg).

Outcome variables related to the specified hypotheses are rate of torque development during 0-100 ms, 0-200 ms, peak RTD, and time to peak force during knee extension and knee flexion for both cases and controls.

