### Descriptive variables

Variables collected for descriptive purposes are data on examination findings, pain intensity and duration, Peak Heigh Velocity, level of sports participation and anthropometrics

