### Statistical considerations

#### Sample size

No previous investigations of rate of torque have been published for adolescents with Osgood-Schlatter. One previous study using the same clinical test setup, equipment, and time-epochs (Early RTD: 0-100 ms, Late RTD: 0-200 ms, and peak RTD) for testing RTD over the hip in young (Under-19) professional soccer players found a mean of 9.57 Nm/kg/s and a standard deviation of 2.6 Nm/s/kg at 0-100 ms.

Considering that peak torque is around 30-50% lower for adolescents (U13 and U14) compared to U19 players, a similar difference might be expected for RTD, and thus we expect a group mean RTD of around 5 or 6 Nm/kg/s at 0-100 ms for asymptomatic adolescents. In adults with non-traumatic knee pain, investigations of RTD during maximal isometric hip extension, has shown differences between symptomatic participants and controls of >50 % during early RTD.

As this study includes RTD of the knee, which is the affected joint, we expect at least similar differences for our primary measure, early RTD at 0-100 ms, this would correspond for example to a between-group difference of 6 vs. 3 Nm/kg/s. We will assume 2.6 Nm/kg/s as an asymptomatic population standard deviation for 0-100 ms. Based on a two-sided two-sample t-test at 80% power and 5% alpha level, 13 participants in each group would thus be needed to detect a 50% between-group difference (R 4.0.2, Foundation for Statistical Computing, Vienna, Austria; RStudio 1.0.153, power.t.t.test package).

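### Group-matched cases and controls aged 9-16 are compared without adjusting for age or sex, although both are matching factors and the planning figures imply an age gradient

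*Combined protocol and SAP*

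**What the plan says.** The abstract's Methods paragraph describes "13 pain free controls matched on sex, age, and sports participation on the group level". The Study design section gives the tolerance: controls are "matched on sex, age (<1 year group difference) and type of sports (weightbearing vs non-weightbearing". The inclusion criteria admit patients aged 9-16. No separate age range is given for controls, so the matching rule alone ties them to that range.

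Under Statistical methods the outcomes "will be compared between groups using an unpaired two-sided students t-test" if residuals look normal; "otherwise the non-parametric alternative, the Wilcoxon rank sum test, will be used". No covariate, regression model or adjusted sensitivity analysis is named.

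Rate of torque development (RTD) is scaled by lever length and bodyweight (Outcome measures). Maturity data have no analytic role: "Variables collected for descriptive purposes are data on examination findings, pain intensity and duration, Peak Heigh Velocity, level of sports participation and anthropometrics".

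The Sample size section reports that a study of Under-19 professional players "found a mean of 9.57 Nm/kg/s and a standard deviation of 2.6 Nm/s/kg at 0-100 ms". It notes that peak torque is about 30-50% lower at U13/U14, suggests that RTD may behave alike, and concludes "we expect a group mean RTD of around 5 or 6 Nm/kg/s at 0-100 ms for asymptomatic adolescents".

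**The concern.** The plan treats age and sex as important enough to match on, then leaves both out of the analysis. This has two consequences.

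- **Residual imbalance.** Group-level matching within one year limits the age difference but does not remove it. If RTD rises with age, older cases would hide part of a true deficit and younger cases would enlarge it. Scaling by lever length and bodyweight deals with size. It does not dispose of the gradient, because the planning means that differ by age are already per kilogram.
- **Precision.** Even with identical mean ages, the spread from 9 to 16 years and the mix of sexes stay in the error term. With 26 participants that matters.

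The comparisons using the asymptomatic knee (hypotheses 3 and 6) are more exposed. They use only those cases who have such a knee, and nothing says that the age tolerance also holds in that subset. The Aim and the Expected results section place the main interest in non-symptomatic limbs and in knee flexion.

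**Working it through.** **Inputs from the Sample size section.** 13 per group, difference 3 (6 vs 3), SD 2.6, two-sided alpha 5%, power 80%; means 9.57 (U19) and 5-6 (younger adolescents).

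**Assumptions, not in the documents.** A linear age gradient over 5-6 years; an age SD of 1.5-2 years in the sample; covariates explaining 10%-30% of variance where stated.

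**1. The plan's own figure.** SE = 2.6 × √(2/13) = 1.02. Noncentral t with 24 df and difference 3 gives power 80.6%. The stated 13 per group is reproduced.

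**2. Implied age slope.** Lower end (9.57 − 6)/6 = 0.60 per year; upper end (9.57 − 5)/5 = 0.91 per year.

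**3. Shift from an age gap.**
- Near one year: 0.6-0.9, which is 0.6/3 = 20% to 0.9/3 = 30% of the planned difference.
- Half a year: 0.3-0.45, which is 10%-15%.

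**4. Rejection rate with no true group effect.** The formula uses SD 2.6. The simulation (20,000 runs per cell, realised gap held fixed) lets the age spread enter the raw standard error and takes 2.6 as either the within-age or the total SD.

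| Age gap | Unadjusted, formula | Unadjusted, simulated | Adjusted, simulated |
|---|---|---|---|
| 1 year | 8.7%-13.5% | 6.0%-10.3% | 4.7%-5.4% |
| Half a year | 5.9%-7.1% | 2.0%-5.1% | 4.7%-5.4% |

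Inflation of false positives is therefore the smaller issue.

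**5. Power for a difference of 3.** The documents do not say how 2.6 relates to the age spread of this sample, so there are three readings. Adjusted figures use 22 df.

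| Reading of SD 2.6 | Unadjusted | Adjusted |
|---|---|---|
| (a) Excludes the age spread: total SD = √(2.6² + (slope × age SD)²) = 2.75-3.16 | 76%-64% | 80.3% |
| (b) Includes it; covariates explain 10% / 20% / 30% | 80.6% | 84% / 88% / 92% |
| (c) SD scales with the mean: 2.6/9.57 × 6 = 1.63; total SD 1.86-2.43 | 98%-86% | 99% |

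Under (a), with a full one-year gap that hides the effect, simulated power is 57%-35% unadjusted and 75%-78% adjusted.

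**6. Cost of adjusting.**
- Useless covariates, balanced groups: 80.6% (24 df) to 80.3% (22 df).
- Useless covariates and a full one-year gap: the variance of the group estimate grows by 1 + 6.5/(24 × age SD²) = 1.07, 1.12 and 1.27 for age SD 2, 1.5 and 1. Power is then 78%, 76% and 70%.
- Hypotheses 3 and 6, assuming 7 such cases against 13 controls: 64.4% (18 df) to 63.8% (16 df).

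**The case against.** The strongest reply is that this is a preference for efficiency resting on assumed numbers. Matching and normalisation already limit confounding, an unpaired test suits group-level matching, and the sample size is correct on its own inputs. All of that is true. The point concerns missing covariates, not missing pairing or a wrong sample size.

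The slope is the weakest link. The plan has no RTD data by age; it borrows a peak-torque deficit that it says only might carry over, and does not say whether that deficit is per kilogram. Taking the 30% end literally gives 9.57 × 0.7 = 6.70 and a slope of (9.57 − 6.70)/6 = 0.48, below the 0.6 used above. A one-year gap then shifts the difference by 16% of 3, with 7.4% rejection under no effect. The 50% end gives (9.57 − 4.79)/5 = 0.96, slightly above the range. So the size is uncertain both ways.

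Other objections also stand in part:
- A gap near one year is the boundary of what is allowed. Even there the shift is under half of the 95% CI half-width of 2.1.
- Under reading (c) nothing is lost against the plan.
- No figure for sex can be taken from the documents.
- A linear age term is itself an assumption, and adjustment loses power if the covariates explain nothing and the groups differ in age.

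These points limit the size. They do not justify leaving two recorded matching factors out of the model when the usual cost is a fraction of a percentage point of power.

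**Conclusion.** The concern holds, as an inexpensive improvement rather than an error that invalidates the plan. It is certain that the comparison is unadjusted and that matching leaves room for an age difference of up to a year. How much this matters depends on an age gradient, an age spread and a reading of SD 2.6 that the documents do not settle, so confidence in the size is medium. In every reading examined with balanced groups, adjustment either raises power or costs about 0.3 percentage points. With a sizeable age gap it also protects the estimate, provided that age is prognostic, as the planning figures suggest. The change should be made before the data are analysed, since adding age and sex after seeing an imbalance would be a data-driven choice.

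**What to change.** In Statistical methods, for hypotheses 1, 3, 4 and 6:

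- Make the primary between-group analysis a linear model of RTD on group, age at test and sex, reporting the adjusted difference with its 95% CI.
- Keep the unadjusted t-test or Wilcoxon test as supportive. When residuals are non-normal, report the Wilcoxon result beside the model, and state in advance that the model is primary.
- Add a sensitivity analysis that replaces age with the maturity estimate from the peak height velocity measurements.
- Leave sport type out of the main model, to hold it to two covariates with 26 participants, and report its distribution by group.
- Report age and sex by group, and separately for the cases who contribute an asymptomatic knee.

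The cost is wording only: the variables are already planned and the model is available in R and jamovi. The statistical price is two degrees of freedom, plus the loss to 78%-70% power in the unfavourable case of a full one-year gap with uninformative covariates.

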## Hypotheses

The hypotheses being tested are

1. that adolescents with Osgood-Schlatter, has a lower knee extension RTD in their affected knee compared to matched controls
2. that adolescents with Osgood-Schlatter, has a lower knee extension RTD in their affected knee compared to their potential asymptomatic knee
3. that adolescents with Osgood-Schlatter, has a lower knee extension RTD in their potential asymptomatic knee compared to matched controls
4. that adolescents with Osgood-Schlatter, has a lower knee flexion RTD in their affected knee compared to matched control
5. that adolescents with Osgood-Schlatter, has a lower knee flexion RTD in their affected knee compared to their potential asymptomatic knee
6. that adolescents with Osgood-Schlatter, has a lower knee flexion RTD in their potential asymptomatic knee compared to matched controls
7. That levels of either early or late rate of torque development is negatively correlated with pain during rate of torque development-testing, countermovement jump height or power, anterior knee pain provocation test score, current pain, pain duration, KOOS child 'Pain', 'Sport/rec' or 'QoL' subscales,

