#### Clinical examination and treatment

The study procedures will be conducted by two examiners (JL and HS). JL will be aware of the case status and conducts the screening and preliminary testing. To avoid bias, examiner HS will be blinded for the case status during trial and will not know the Numerical pain Rating Scale-scores (NRS, 0-10, 'no pain' to 'worst pain imaginable') of the participants during testing. To strengthen the inter-reliability, the examiners will not change roles during the study.

The session starts with JL examining the potential participant in the OSD-case group, for Osgood-Schlatter. If the Osgood-Schlatter diagnosis is made, the participant is then enrolled. For the potential participant in the control group, JL screens for potential injury or pain in relation to the knee joint. In the absence of relevant pathology, the control-participant is enrolled.

Then, JL measures length of the lever arm and variables for peak hight velocity assessment. Participants will then answer the patient-reported outcome measures together with their parent/guardian.

For the rate of force development tests, HS will enter the room and conduct the tests as described below. For each attempt the participant will write down their NRS-rating on a piece of paper, out of sight from HS.

Before the rate of force development test is conducted, the participants are told that they can always abort the test, if they perceive that pain rises to such a degree that they can't continue the

testing, or they start feeling fearful or uncertain of their symptoms. They are ultimately told that potential pain felt during testing are not harmful and will subside within 24 hours, as is our experience from multiple earlier conducted tests.

HS leaves the room, for JL to conduct the Anterior Knee Pain Provocation test and save the NRS results.

HS returns to conduct the Counter Movement Jump Test, again blinded for the participants NRS-scores, which are written down on a piece of paper. HS leaves the room, and JL either treats the patient (case-group) or hands out compensation for participating (control-group).

Cases and controls will be instructed not to take any pain medication 24 hours prior to any assessment to ensure that this does not affect measurements.

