### Knee extension

The participant is sitting with  $90^\circ$  hip flexion, knee flexed approximately  $60^\circ$ , with test leg resting in testers hand, and feet free of the floor. They will be instructed to hold onto the back of the examination table and keep their upper body upright. A strap fixated to the bottom of the examination bed, is used to fixate the handheld dynamometer anteriorly on the shin, corresponding to the line of lever demarcation. If the participant feels the metal of the gauge on their shinbone through the padding of the dynamometer, extra padding will be placed on the shin.

The participant will be instructed to *press against the dynamometer as fast and hard as possible, and to keep pushing until instructed to relax* (approximately 3-4sec.). Standardized verbal instruction is provided before each trial by the tester: *3-2-1-go-push-push-push and relax*. For the knee flexion, the participant will be instructed to bend their knee, and for the extension, to straighten the leg.

Participants will perform two test trials: one at 50% of self-estimated maximal force, and one at 100%. The assessor will hold the leg in starting position to allow full rest between trials, lasting 1-minute. Three maximal attempts are recorded. One tester will hold the dynamometer and instruct the patient (HS), while one tester (JL) manage data collection software (Hoggan Health Industries 2000, version 11.0.1, Quest Medical Group, Inc.). The order of the movements is decided by coin

toss. The affected leg is tested first in each movement. In the control group the affected leg will be decided by coin toss before tester HS enters the room.

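### Hypotheses 2 and 5 compare two knees of the same adolescent but have no paired test, and the affected leg is always tested first, so limb and test order cannot be separated

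*Combined protocol and SAP*

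**What the plan says.** The Hypotheses section lists seven hypotheses. Two of them are comparisons within one person. Hypothesis 2 is that a case "has a lower knee extension RTD in their affected knee compared to their potential asymptomatic knee"; hypothesis 5 is that a case "has a lower knee flexion RTD in their affected knee compared to their potential asymptomatic knee". The data for a within-person analysis are planned: "Testing will include bilateral rate of torque development measurements of knee extension and flexion" (Methods, in the opening summary).

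The Statistical methods section says that outcomes will be "compared between groups using an unpaired two-sided students t-test, assuming the residuals will be normally distributed". If normality fails, the Wilcoxon rank sum test replaces it. The section promises between-group differences. No paired t-test, signed-rank test or mixed model appears in the document.

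The Knee extension section sets the order of testing. The order of the two movements is tossed for, but the order of the legs is not: "The affected leg is tested first in each movement". For controls, "In the control group the affected leg will be decided by coin toss", after which they follow the same leg order.

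**The concern.** There are two linked gaps.

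1. **No test.** The tests named are for independent samples and are tied to comparisons between groups. Two knees of one adolescent are not independent samples, so the analysis of hypotheses 2 and 5 would be chosen after the data are seen. The same section justifies the absence of a multiplicity correction by prior specification, so the omission matters.

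2. **Aliasing with order.** In every case the affected knee is the first-tested knee and the asymptomatic knee is the second. A second-leg gain from learning or warm-up would look like a deficit in the affected knee. A second-leg loss from fatigue would hide a real one. More participants would not resolve this, and neither would a paired test by itself.

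**Working it through.** **The plan's own figure.** The Sample size section gives 6 vs 3 Nm/kg/s, SD 2.6, two-sided 5% alpha and 80% power. The standardized difference is 3/2.6 = 1.154. The noncentral-t two-sample calculation needs 12.83 per group, rounded up to 13, with power 80.6%. The stated 13 per group is reproduced, but it concerns cases versus controls only. No sample size is given for hypotheses 2 and 5.

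**What the within-case contrast estimates.** Let D = asymptomatic minus affected knee. Under the fixed order this is also second minus first leg. With true limb deficit δ and second-leg shift s, E(D) = δ + s. Nothing measured within cases separates δ from s.

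**Inputs**
- SD 2.6 (Sample size section), applied to both limbs.
- Between-limb correlation r = 0.3 to 0.8: not in the documents, assumed.
- Order shift s of 0.3 or 0.6, i.e. 5% or 10% of 6: not in the documents, assumed.
- True limb deficit δ = 1.5 (assumed), or 3 (the plan's between-group figure).
- 13 pairs, or 8 (assumed) if some cases are bilateral and have no asymptomatic knee. The anterior knee pain provocation test refers to a most affected knee, so bilateral cases are foreseen.

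**Formula.** SD of D = 2.6·√(2(1−r)), which is 3.08, 2.60, 2.01 and 1.64 at r = 0.3, 0.5, 0.7 and 0.8. The noncentrality of the paired t-test is (δ + s)·√n / SD of D, with n − 1 degrees of freedom.

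Rejection probability of the paired t-test under the fixed order:

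| δ | s | n | r=0.3 | r=0.5 | r=0.7 | r=0.8 |
|---|---|---|---|---|---|---|
| 0 | +0.3 | 13 | 0.062 | 0.067 | 0.079 | 0.093 |
| 0 | +0.6 | 13 | 0.099 | 0.120 | 0.168 | 0.228 |
| 0 | +0.3 | 8 | 0.057 | 0.059 | 0.066 | 0.073 |
| 0 | +0.6 | 8 | 0.077 | 0.088 | 0.113 | 0.146 |
| 1.5 | 0 | 13 | 0.366 | 0.481 | 0.694 | 0.855 |
| 1.5 | −0.6 | 13 | 0.163 | 0.210 | 0.317 | 0.443 |
| 1.5 | 0 | 8 | 0.223 | 0.292 | 0.444 | 0.603 |
| 1.5 | −0.6 | 8 | 0.111 | 0.136 | 0.195 | 0.268 |
| 3 | 0 | 13 | 0.897 | 0.968 | 0.998 | 1.000 |
| 3 | −0.6 | 13 | 0.733 | 0.863 | 0.976 | 0.998 |
| 3 | 0 | 8 | 0.659 | 0.799 | 0.948 | 0.992 |
| 3 | −0.6 | 8 | 0.477 | 0.613 | 0.823 | 0.940 |

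**With leg order tossed instead** (200,000 simulated studies): the plain paired test rejects a true null in 4.9–5.1% of studies for shifts of 0, 0.3 and 0.6. The shift becomes extra variance instead of bias.

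**If the named unpaired test were used for hypotheses 2 and 5** (400,000 simulated studies): its true type I error at 13 pairs would be 2.1%, 0.86%, 0.15% and 0.03% across the four correlations. That errs on the conservative side. The plan does not say it would be used this way.

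**The case against.** - **Secondary status.** The aim, the sample size and the planned reporting all concern cases versus controls, and hypotheses 2 and 5 carry no power claim. This stands and limits the weight of the point.
- **The controls already rescue the contrast.** They follow the same leg order with a coin-tossed leg, so the planned data can estimate a shared order effect. This is right, and it largely protects hypotheses 1, 3, 4 and 6 from ordinary order effects. But the plan does not use the controls in this way for hypotheses 2 and 5. The correction also assumes that both groups have the same order effect, and it costs power.
- **The size of the shift is assumed.** This also stands. The 23% needs a 10% shift, r = 0.8 and 13 pairs together; at a 5% shift and r = 0.5 the figure is 6.7%. Practice trials and one-minute rests should make a shift smaller. They do not show that it is zero, and the aliasing itself does not depend on any assumed number.
- **A paired test is the obvious choice.** Probably so, but then it costs one sentence to say it, and it leaves the order problem untouched.
- **The analysis strategy was also published with the registration.** That text is not available here, so the statement that no paired test is assigned is confined to this document.

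**Conclusion.** The concern holds, and the plan should be changed on this point. Both parts follow from the text: no suitable test is named for hypotheses 2 and 5, and in cases limb and test position are the same variable. As written, an estimate for these hypotheses cannot be attributed to the limb rather than to being tested first or second.

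The size depends on the assumed correlation (0.3–0.8) and shift (0.3–0.6). False support rises from 5% to 6–23% with 13 pairs, or 6–15% with 8. Power for a true 1.5 under a second-leg loss of 0.6 falls from 37–85% to 16–44%, or from 22–60% to 11–27%. For a true 3 the fall is smaller: from 90–100% to 73–100%, or from 66–99% to 48–94%. The direction of any bias is unknown.

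The main case-control comparison is not undermined. A minor related gap is that the plan does not say which control leg is the comparator in hypotheses 3 and 6; the second-tested leg is the natural reading. Pain carried over to the second leg in cases only is a possible rival explanation there, of unknown size.

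**What to change.** **In any event (Statistical methods).** Add: *Hypotheses 2 and 5 will be tested in cases with one asymptomatic knee by a two-sided paired t-test (Wilcoxon signed-rank as fallback), reporting the mean within-person difference, 95% CI and number of pairs. In hypotheses 3 and 6 the control comparator is the non-designated leg (the second-tested leg if the fixed order is kept).*

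**If testing is not complete (Knee extension section).** Set leg order by coin toss in both groups. The unblinded examiner should do and record this before the blinded examiner enters. Keep the plain paired test as the main analysis. Use the order-adjusted estimate (within-person difference regressed on order coded +1/−1) as a sensitivity analysis only.

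**If testing was done in the fixed order** (the summary expected completion by May 2023). Add a two-sample t-test of the cases' second-minus-first-leg difference against the controls'. This removes an order effect shared by both groups. Describe pain during second-leg testing from ratings already planned: "For each attempt the participant will write down their NRS-rating on a piece of paper", and "The outcome measures are rate of torque development and NRS-values in relation to the force-measurements". State residual order confounding as a limitation.

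**Cost.** Two sentences and, if testing continues, one recorded coin toss per participant; no added participants or visits. The statistical costs below for the within-case contrast are for a true difference of 1.5 and r = 0.3–0.8:
- The order term lowers power from 37–85% to 34–82% (13 pairs) or from 22–60% to 19–52% (8 pairs). It cannot be fitted when all tosses agree: 2·0.5⁸ = 0.8% of studies with 8 pairs.
- With tossed order, a real shift of 0.6 leaves the plain paired test with 35–81% power (13 pairs) or 22–55% (8 pairs).
- The control-corrected comparison keeps a 5% type I error if the order effect is shared. Its power is 22–61% (13 vs 13) or 18–49% (8 vs 13). With 13 cases, its 95% CI half-width is 2.49 (r = 0.3) to 1.33 (r = 0.8), against 1.86 to 0.99 for the paired test.
- For the main contrast (6 vs 3, 13 per group), tossing leg order moves power from 80.6% to about 80% at a shift of 0.6, and to 79.1% at a shift of 1.0.

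### Cohen's d is planned without a small-sample correction: it runs about 3 to 5% high in the case-control contrasts, and 3 to 19% high in the within-case contrasts depending on inputs the plan does not give

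*Combined protocol and SAP*

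**What the plan says.** Statistical methods states that the outcome variables "will be compared between groups using an unpaired two-sided students t-test", with the Wilcoxon rank sum test as the fallback. On reporting it says "Data will be reported with between-group differences", followed by "standardized effect sizes based on Cohens d", exact p-values and 95% confidence intervals. It mentions no small-sample correction and does not say which standard deviation divides the difference.

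Study design sets the numbers: "13 participants in the OSD-group, and 13 in control group". The Hypotheses section then lists three kinds of contrast for extension and flexion:

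- affected case knee against controls (hypotheses 1 and 4);
- asymptomatic case knee against controls (3 and 6);
- the two knees of the same case (2 and 5). Hypothesis 2, for example, is that a case "has a lower knee extension RTD in their affected knee compared to their potential asymptomatic knee".

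The asymptomatic knee is described only as a potential one, and the inclusion criteria do not require unilateral pain. The section on the anterior knee pain provocation test allows for one knee being worse than the other. Cases with pain in both knees are therefore admitted. The documents neither state nor limit how many cases will have an asymptomatic knee.

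**The concern.** The sample standard deviation in the denominator of d makes d too large on average, by a factor that depends only on its degrees of freedom. At 24 degrees of freedom the excess is slight. At the few degrees of freedom of a paired contrast in a handful of unilateral cases it is not.

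What is at stake is the standardised point estimate. The Sample size section notes that no rate-of-torque data have been published for this group, so later studies may well borrow these estimates. An inflated d leads such a study to plan too few participants. The bias runs in one direction, its exact factor is known, and the plan leaves it in.

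**Working it through.** **Inputs from the documents.** 13 cases and 13 controls (Study design); "between-group difference of 6 vs. 3 Nm/kg/s" and "We will assume 2.6 Nm/kg/s as an asymptomatic population standard deviation for 0-100 ms" (Sample size); unpaired t-test and Cohen's d (Statistical methods); the contrasts in hypotheses 1 to 6.

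**Inputs assumed.** The number m of cases with an asymptomatic knee is not given; 13 down to 6 is shown. The standardiser for hypotheses 2 and 5 is not given; two readings are shown.

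**Step 1: the plan's own figure.** The planning effect is 3 / 2.6 = 1.154. The basis is stated as "Based on a two-sided two-sample t-test at 80% power and 5% alpha level". With the noncentral t distribution, power is 0.771 at 12 per group and 0.806 at 13, so 13 per group is reproduced.

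**Step 2: the bias factor.** The exact factor is J(df) = Γ(df/2) / [√(df/2) × Γ((df−1)/2)]. The expected value of d is the true value divided by J, so the inflation is 1/J − 1.

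- df 24: J = 0.9684; 1/0.9684 − 1 = 3.3%.
- df 17: J = 0.9551; 1/0.9551 − 1 = 4.7%.
- df 12: J = 0.9359; 1/0.9359 − 1 = 6.8%.
- df 5: J = 0.8407; 1/0.8407 − 1 = 18.9%.

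**Step 3: each contrast.** Hypotheses 1 and 4 have 13 + 13 − 2 = 24 df, hence 3.3%. The others depend on m:

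| m | H3, H6: m v 13, df = m + 11 | H2, H5 with paired d, df = m − 1 | H2, H5 with unpaired d, df = 2m − 2 |
|---|---|---|---|
| 13 | 24 df, 3.3% | 12 df, 6.8% | 24 df, 3.3% |
| 10 | 21 df, 3.8% | 9 df, 9.4% | 18 df, 4.4% |
| 8 | 19 df, 4.2% | 7 df, 12.6% | 14 df, 5.8% |
| 6 | 17 df, 4.7% | 5 df, 18.9% | 10 df, 8.4% |

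Paired d here means the mean difference divided by the SD of the differences. The last column takes the independent-samples formula at face value. Two knees of one participant are correlated, so those figures are nominal and, if anything, low. With only five unilateral cases the last two columns would be 25.3% and 10.8%.

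**Step 4: effect on a later sample size.** Required n varies roughly as 1/d², so planning on the expected uncorrected d understates n by 1 − J²: 1 − 0.9684² = 6% at 24 df, 1 − 0.9359² = 12% for 13 pairs, and 1 − 0.8407² = 29% for six pairs.

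**Step 5: size beside sampling error.** An observed d of 1.154 in 13 v 13 becomes g = 1.154 × 0.9684 = 1.117, a change of 0.04, while its 95% CI runs from about 0.31 to 1.98. An observed paired d of 0.5 in six pairs becomes 0.5 × 0.8407 = 0.42, a change of 0.08, while its 95% CI runs from about −0.38 to 1.33.

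**The case against.** The case against acting has four parts.

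**The larger figures describe a statistic the plan does not define.** Statistical methods has no paired test and no paired d, and the documents give no count of unilateral cases. This stands. The upper end of the range is conditional on both and should never be quoted without them. If all 13 cases have an asymptomatic knee, even the paired d is only 6.8% high.

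**The bias is trivial next to the intervals.** It is small, as Step 5 shows. But a wide interval is no reason to keep a known one-sided bias that one multiplication removes.

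**The plan already protects the reader.** It reports raw differences, exact p-values and intervals, and promises the full data and code, so anyone can compute g. The study itself was planned from raw means and an SD, not from a published d. That limits the harm, but it does not show that the uncorrected d is the better number to print.

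**The correction does not make the effect sizes comparable.** A reader might infer that the unequal bias is what prevents the within-case and case-control effects from being set side by side, and that Hedges' g would cure it. The documents do not support that. A paired d and a between-group d have different denominators. With equal SDs their ratio is 1/√(2(1 − r)), where r is the correlation between knees: 0.85 at r = 0.3, 1.00 at r = 0.5, 1.58 at r = 0.8 and 2.24 at r = 0.9. The documents give no r, so these values are assumptions. The standardiser can therefore matter more than the bias, and in either direction, and J does not touch it. Reading a true value of 0.80 as 0.80 / 0.9684 = 0.83 in hypothesis 1 and 0.80 / 0.8407 = 0.95 in six pairs is correct for each design separately, but 0.80 is not the same quantity in the two designs unless r = 0.5.

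**Conclusion.** The point holds as a minor reporting improvement. For the case-control contrasts the overstatement is 3.3% (hypotheses 1 and 4) and 3.3 to 4.7% (hypotheses 3 and 6, with 13 down to 6 asymptomatic case knees). Hypotheses 3 and 6 address the asymptomatic limb, which the plan names as part of its main interest, so the bias there is slight.

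For hypotheses 2 and 5 the size cannot be fixed from the documents. It is about 7 to 19% with a paired d and about 3 to 8% (nominal) with the unpaired test as written, both for an assumed 13 down to 6 unilateral cases. A flat statement that the within-case effects are inflated by a tenth to a fifth would go beyond what the plan shows.

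Tests, p-values, raw differences and their intervals are unaffected.

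**What to change.** In Statistical methods, replace Cohen's d with Hedges' g, defined as d multiplied by the exact factor J for its degrees of freedom, with a 95% CI for every comparison. State which standard deviation is the denominator for hypotheses 2 and 5; J cannot be applied there until that is settled. Report the degrees of freedom for each estimate and the number of cases with an asymptomatic knee. Add a sentence that within-case and case-control effect sizes use different standardisers, where that is so, and should be compared in Nm/s/kg.

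The cost is a few lines of text and one multiplication per estimate. No new data, participants or tests are needed, and no p-value or raw difference changes.
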